**The Role of Narrow Band Imaging (NBI)
Bronchoscopy in Detecting Bronchial Squamous
Dysplasia in Lung Cancer**

[name]

**Department of Pulmonology and Respiratory Medicine, Persahabatan
Hospital, Faculty of Medicine Universitas Indonesia**

ID: ND-552/UN2.RST/PPM.00.00/2023

October 26th, 2023

1. Title

The Role of Narrow Band Imaging (NBI) Bronchoscopy in Detecting Bronchial Squamous Dysplasia in Lung Cancer

2. Ethical clearance

The date of approval from Health Research Ethics Committee Faculty of Medicine Universitas Indonesia, [name] General Hospital is 23rd March 2023 (KET-361/UN2.F1/ETIK/PPM.00.02/2023)

3. Study Protocol

- Problem Statement

1. What are the NBI imaging criteria for detecting bronchial squamous dysplasia in lung tumor patients?
2. How does the diagnostic profile of NBI bronchoscopy compare with standard bronchoscopy (white light bronchoscopy, WLB) in detecting bronchial squamous dysplasia in lung tumor patients?
3. Can the addition of NBI to standard bronchoscopy procedures improve diagnostic accuracy in detecting bronchial squamous dysplasia in lung tumor patients?

- Research Objectives

This research aims to determine the diagnostic profile (area under the curve, AUC; sensitivity, specificity, positive predictive value, and negative predictive value) of NBI bronchoscopy in detecting bronchial squamous dysplasia in lung tumor patients.

4. Method

- Study Design

This is an observational diagnostic study. The research was conducted at the bronchoscopy suite of Persahabatan Hospital, where bronchoscopy procedures, bronchial biopsy collection, and specimen handling took place. The histopathological examinations were carried out in the Department of Anatomical Pathology, Faculty of Medicine, Universitas Indonesia, The patient recruitment time ranges from March to December 2023.

- Population

The target population consists of all lung tumor patients. The accessible population consisted of lung tumor patients who underwent bronchoscopy procedures at Persahabatan Hospital from March to December 2023.

- Study participants

- The study participants comprised individuals from the accessible population who met the research participants acceptance criteria and provided informed consent. The consecutive sampling method was employed.
- **Study participants calculation**

The study participants size was calculated using the diagnostic research sample size formula. The minimum sample size required was 110 participants
 - **Inclusion criteria**
 1. Patient aged > 18 years undergoing bronchoscopy for diagnostic evaluation of lung tumors
 2. Recent radiological examinations, including both chest X-ray and chest CT scans, within the last month, revealed a central lesion of lung cancer
 - **Exclusion criteria**
 1. Refusal to provide informed consent
 2. Contraindications to bronchoscopy
 - **Participants selection**

Screening was conducted on all lung tumor patients scheduled for bronchoscopy procedures, and the participants selection was carried out in accordance with the inclusion and exclusion criteria
 - **Sampling Technique**

The preparation and execution of bronchoscopy and bronchial biopsy were performed in accordance with the standard operating procedures (SOP) at Persahabatan Hospital. The bronchoscopy and bronchial biopsy procedures were conducted by a single operator, the principal investigator. The bronchoscopy procedure uses general anesthesia. The flexible fiberoptic bronchoscopy was performed using an Olympus EVIS EXERA III with a Xenon light source, model CLV-190, and BF-1TQ170 series scope. The Boston Scientific Radial Jaw™ 4 disposable lung biopsy forceps were employed. Bronchoscopy was initially performed under the white light, followed by the activation of the NBI feature for airway inspection. Biopsies were obtained from areas identified through NBI bronchoscopy findings. Furthermore, the criteria for bronchoscopy images suspected for dysplasia included the presence of dotted vessels, capillary loops, tortuous vessels, and abrupt ending vessels. No biopsies were conducted on infiltrative neoplasms or tumors. The biopsied tissue was then preserved in a separate 10% formalin solution. Tissue processing involved paraffin embedding and Hematoxylin-Eosin staining. Tissue processing was performed using a Tissue Processor machine. Following tissue processing, paraffin blocks were created and sectioned. Hematoxylin-Eosin staining was then performed. Diagnosis of squamous bronchial dysplasia (pre-cancer lesion) was made by a specialist in Anatomical Pathology.

5. Statistical Analysis Plan (SAP)

The research data were recorded on research forms and subsequently entered into SPSS 26 software. the bivariate analysis was conducted between each vascular pattern based on NBI bronchoscopy and the histopathological result. The descriptive data will be presented by the text and tables consist of the basic characteristics of the study participants and research variables. The multivariate analysis was performed on all vascular patterns based on NBI bronchoscopy and histopathological results. Furthermore, a pre-cancer prediction score was generated. An analysis of the AUC (area under the curve) of the squamous dysplasia prediction model form NBI bronchoscopy findings was conducted with a significance level set at $p < 0.05$

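### Two of the three study questions need a white-light (WLB) result, but no inferential or model-based analysis in the SAP uses one, and NBI-directed biopsy means a sensitivity comparison cannot simply be added

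*Combined protocol and SAP*

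**What the plan says.** The Problem Statement has three questions. The first concerns NBI imaging criteria. The second asks "How does the diagnostic profile of NBI bronchoscopy compare with standard bronchoscopy (white light bronchoscopy, WLB". The third asks "Can the addition of NBI to standard bronchoscopy procedures improve diagnostic accuracy in detecting bronchial squamous dysplasia".

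The Research Objectives section is narrower. It lists AUC, sensitivity, specificity, PPV and "negative predictive value) of NBI bronchoscopy in detecting bronchial squamous dysplasia in lung tumor patients". No comparator is named.

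Under Sampling Technique, "Bronchoscopy was initially performed under the white light, followed by the activation of the NBI feature for airway inspection". No definition of a WLB-positive area is given, and no recorded WLB result is described. On histology: "Biopsies were obtained from areas identified through NBI bronchoscopy findings". On suspicion: "the criteria for bronchoscopy images suspected for dysplasia included the presence of dotted vessels, capillary loops, tortuous vessels, and abrupt ending vessels". On the operator: "The bronchoscopy and bronchial biopsy procedures were conducted by a single operator, the principal investigator".

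The SAP plans a bivariate analysis of each NBI vascular pattern against histopathology, a multivariate analysis of all the NBI patterns, a prediction score, and the AUC of the NBI-based model. It also plans descriptive tables of baseline characteristics and of study variables that it does not list. WLB does not appear in the SAP.

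**The concern.** Questions 2 and 3 cannot be answered without a WLB result for each unit analysed, and the SAP plans no inferential or model-based use of one. Either the two questions are left open, or they are answered by a comparison devised after the data are in.

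The second outcome is the more harmful. The obvious improvisation is a paired test of NBI against WLB sensitivity in the biopsied material. If only areas that NBI picked out have histology, one of the two tests has chosen the sample on which both are judged. The same selection limits the NBI-only Objective: sensitivity, specificity and NPV need histology from areas that NBI passed over.

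**Working it through.** **Step 1. Questions against analyses.**

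| Question | Needs | Planned analysis using it |
|---|---|---|
| 1. NBI criteria | NBI patterns, histology | bivariate, multivariate, score, AUC |
| 2. NBI against WLB | a WLB result per unit, histology not chosen by NBI | none |
| 3. WLB plus NBI against WLB | a WLB result as baseline model | none |

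Two of three questions have no planned analysis. No assumed number enters this step.

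**Step 2. The plan's own figure.** The only figure is the sample size: "The minimum sample size required was 110 participants". Its inputs are not given, so it cannot be reproduced. A precision formula, N = z²·p(1−p)/(d²·prevalence), reaches about 110 from quite different inputs: p 0.85, d 0.08, prevalence 0.7 gives 110; p 0.90, d 0.08, prevalence 0.5 gives 109. The 110 therefore does not show whether a comparison was ever sized. The point does not rest on it.

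**Step 3. Why a sensitivity test cannot be bolted on.** The documents give no sensitivities, and the unit of analysis is not stated. Everything below assumes area-level analysis, histology only in NBI-selected areas, and illustrative inputs.

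*Definition (a): NBI-positive means selected for biopsy under NBI.* Among verified areas NBI sensitivity is then 100% and specificity 0% by construction. With sN and sW the true sensitivities and J the probability that both detect a dysplastic area, apparent gain = 1 − J/sN, and false part = apparent − (sN − sW).

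| sN | sW | J | Apparent | True | False |
|---|---|---|---|---|---|
| 0.60 | 0.60 | 0.36 (independent) | +40 | 0 | 40 |
| 0.60 | 0.60 | 0.50 | +17 | 0 | 17 |
| 0.60 | 0.60 | 0.55 | +8 | 0 | 8 |
| 0.60 | 0.60 | 0.60 (full overlap) | 0 | 0 | 0 |
| 0.80 | 0.50 | 0.40 | +50 | +30 | 20 |
| 0.50 | 0.60 | 0.30 | +40 | −10 | 50 |

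(Percentage points.) In the last row the worse test appears 40 points better.

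*Definition (b): NBI-positive is set by the prediction score*, which is closer to the SAP. Among dysplastic areas let v be the share biopsied, p the share score-positive (all of them biopsied), w the share WLB-positive, and m the share WLB-positive but not biopsied. Apparent difference = (p − w + m)/v; false part = (p − w)(1/v − 1) + m/v.

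- v 0.8, p = w = 0.6, m = 0.12: 0.12/0.8 = +15 points, all false.
- Same with m = 0.05: about +6. With m = 0: 0.
- v 0.8, p 0.5, w 0.7, m = 0: apparent −0.20/0.8 = −25, true −20, false −5.

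The bias can run either way.

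**Step 4. The NBI-only Objective.** Assume four independent patterns, each present in 40% of dysplastic and 10% of other areas, biopsy if and only if at least one is present, and score-positive at two or more. P(at least one) is 1 − 0.6⁴ = 0.870 and 1 − 0.9⁴ = 0.344.

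- Sensitivity: 0.525 over all areas; 0.525/0.870 = 0.603 among biopsied areas.
- Specificity: 0.948 over all areas; 1 − (1 − 0.948)/0.344 = 0.848 among biopsied areas, from unrounded values.
- AUC of the pattern count: 0.834 over all areas; 0.738 among biopsied areas.

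With 20% instead of 10% in other areas, specificity goes from 0.819 to 0.694 and AUC from 0.726 to 0.666.

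**Step 5. Precision of a conditional alternative.** If WLB calls exist, the share of dysplastic biopsied areas that were WLB-normal can be estimated. Near one half, exact 95% intervals are 16–84% (4/8), 27–73% (10/20), 31–66% (16/33) and 36–64% (25/50).

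**The case against.** The strongest reply is that the Research Objective is the formal aim, it is NBI-only, and the SAP addresses its AUC; the problem statements are then background, and the gap closes by rewording. That is fair as to cost, and withdrawal is one of the remedies below. It does not remove the inconsistency: the two questions stand in the plan and invite an unplanned answer.

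Other limits also stand. The SAP's descriptive tables cover unlisted variables, and the research forms are not visible, so WLB findings may have been recorded and may be tabulated. A descriptive table would still not answer either question. The Method does not say that biopsies came only from NBI-identified areas, and the hospital's operating procedure is not shown. The suspicion criteria are said to include the four named patterns, so the list may not be complete, and the SAP does not list the patterns it models. Step 4's biopsy rule is therefore an assumption.

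A reader might go further and infer that the comparison is bound to favour NBI, or that NBI sensitivity will come out at 100%. The documents do not support this. It follows only at area level under definition (a); under definition (b) the direction is not fixed, and neither the unit nor the definition of NBI-positive is stated. Nor do the documents show that WLB calls were never made; they only do not describe them.

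**Conclusion.** The point holds and should be fixed before analysis. Its weight rests on what the text settles: 2 of 3 stated questions have no planned inferential or model-based analysis.

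The second part is conditional. On the natural reading that only NBI-identified areas have histology, comparative sensitivity cannot be identified from these data, and NBI sensitivity, specificity and NPV can be read only among biopsied areas. The bias figures (0 to 40 points with equal sensitivities of 60% under definition (a); −5 to +15 in the cases shown under definition (b)) rest on assumed inputs and an assumed unit. They show why a sensitivity comparison should not be improvised. They do not predict this study's error.

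**What to change.** 1. State in the SAP the unit of analysis, the definition of a WLB-positive area, and whether that call was recorded before NBI was activated. Record it that way for any participants still to come. Do not reconstruct calls afterwards: one operator performed every procedure, so a later WLB call would be made knowing the NBI view.
2. If no such calls exist, withdraw Problem Statements 2 and 3 or declare them unanswerable from these data. Decide this on whether calls were recorded, not on the histology results.
3. If calls exist, reword both statements as conditional on NBI-selected biopsied areas.
   - Statement 2: report the number and proportion of dysplastic areas that were WLB-normal, with an exact 95% CI, and the extra non-dysplastic biopsies per extra dysplasia found. The intervals in Step 5 show the precision to expect.
   - Statement 3: compare a model with the WLB call alone against one with the call plus NBI patterns by a likelihood-ratio test, and report the change in AUC after bootstrap optimism correction. In a simulation with assumed inputs (four pure-noise patterns, 20 dysplastic and 90 other areas) the uncorrected AUC rose by about 0.08 on average and the corrected one by about 0.01.
   - Allow for clustering if patients contribute more than one area.
4. Do not test an NBI-versus-WLB sensitivity difference on these data.
5. Report PPV and the score's AUC as conditional on biopsied areas. Do not report NBI sensitivity, specificity or NPV as whole-airway or patient-level values unless areas without NBI suspicion were also biopsied.

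Cost: one SAP paragraph and a bootstrap run if calls exist, or two statements reworded or withdrawn if not, plus a sentence qualifying the Objective. No extra biopsy or staff is needed, beyond noting the WLB call for any remaining participants. The downside is that the claim narrows from comparative accuracy to conditional added yield, or is dropped, and the Objective loses whole-airway sensitivity, specificity and NPV.

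### White light always precedes NBI with one operator, so the plan measures NBI read with knowledge of white light, not NBI uninformed by it

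*Combined protocol and SAP*

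**What the plan says.** In the combined protocol and SAP, section 4 (Method, Sampling Technique) gives one order for all patients: "Bronchoscopy was initially performed under the white light, followed by the activation of the NBI feature for airway inspection". It adds: "The bronchoscopy and bronchial biopsy procedures were conducted by a single operator, the principal investigator". On tissue sampling it says: "Biopsies were obtained from areas identified through NBI bronchoscopy findings". The positivity criteria are four vascular signs: "the criteria for bronchoscopy images suspected for dysplasia included the presence of dotted vessels, capillary loops, tortuous vessels, and abrupt ending vessels". No criteria for a positive white-light finding are given.

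Section 3 (Research Objectives) seeks the AUC, sensitivity, specificity and predictive values "of NBI bronchoscopy in detecting bronchial squamous dysplasia in lung tumor patients". Of the three Problem Statements in section 3, two bear on the relation between NBI and WLB. The second sets the tests against each other: "How does the diagnostic profile of NBI bronchoscopy compare with standard bronchoscopy (white light bronchoscopy, WLB". The third asks about an add-on: "Can the addition of NBI to standard bronchoscopy procedures improve diagnostic accuracy in detecting bronchial squamous dysplasia".

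Section 5 (SAP) relates the NBI vascular patterns to histology one at a time and then jointly, builds a prediction score and reports its AUC. It contains no white-light variable and no test of NBI against WLB.

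**The concern.** The operator has just seen the airway under white light when NBI is switched on. An area that already looked suspicious may be inspected longer and called more readily under NBI. The NBI pass also benefits from being a second look. The documents describe nothing that separates the two readings: no alternation of order, no masked second reader, and no white-light call closed before NBI. That both looks fall in one session is implied by the switching-on of a feature rather than stated.

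What is at stake is which test the results describe. The objective does not mention WLB, and Problem Statement 2 treats NBI and WLB as two tests to be compared. If the published profile is read as a property of NBI itself, or set beside a white-light figure, part of what is credited to NBI may come from the preceding white-light look. Because biopsies follow the NBI findings, the same influence can reach the selection of tissue sent to pathology, and so the data behind the score and its AUC.

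**Working it through.** The plan gives no figure on this point to reproduce. Its minimum of 110 participants is stated without inputs and has no bearing on reading order. The check is a reading of the sections against each other, followed by an illustration on assumed values to settle direction.

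**1. What is observed.** Every patient contributes an NBI reading made after a white-light look by the same operator. An uninformed profile needs NBI readings made without that look, and no patient supplies one. More patients would not help.

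**2. Which test this is.** An either-positive combination of WLB and NBI would count areas flagged by white light alone. Biopsies come from NBI-identified areas and section 5 models only NBI patterns, so white-light-only areas do not enter. The quantity measured is NBI read with knowledge of WLB.

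**3. Direction.** All inputs here are assumed, because the documents give none.
- Sensitivity of NBI alone: 0.70. Sensitivity of WLB alone: 0.50. Misses independent.
- Specificity, equal for both tests: 0.70 in one case, 0.90 in the other. False positives independent.
- c is the share of areas flagged by white light, and missed or cleared by NBI alone, that are called positive under NBI because of the earlier look.

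Formulas:
- Sensitivity credited to NBI = 0.70 + c × (1 − 0.70) × 0.50 = 0.70 + 0.15c.
- Specificity credited to NBI = Sp − c × (1 − Sp) × Sp. This is 0.70 − 0.21c in the first case and 0.90 − 0.09c in the second.
- Net change = change in sensitivity plus change in specificity.

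| c | Sensitivity (from 0.70) | Specificity (from 0.70) | Net change | Specificity (from 0.90) | Net change |
|---|---|---|---|---|---|
| 0.25 | 0.7375 | 0.6475 | −0.015 | 0.8775 | +0.015 |
| 0.5 | 0.775 | 0.595 | −0.03 | 0.855 | +0.03 |
| 1 | 0.85 | 0.49 | −0.06 | 0.81 | +0.06 |

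Sensitivity rises and specificity falls in every row. The sign of the net change depends on the assumed specificity.

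**4. Dependence between the tests.** The 0.15 is the share of dysplastic areas seen by white light but missed by NBI, and it follows from independent misses. If every area WLB detects is also one NBI alone would detect, that share is 0 and credited sensitivity stays at 0.70 for any c. One operator viewing the same mucosa may well have correlated misses, and the documents do not say how strongly.

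**5. Observability.** These sensitivities have all dysplastic areas as denominator. With only NBI-identified areas biopsied, dysplasia elsewhere has no histology, so the study could not observe 0.70 or 0.85. The table shows direction only and does not estimate the effect in this study.

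**The case against.** The strongest reply is that the harm is conditional. Section 5 plans no NBI-versus-WLB contrast, so the comparison that reading order would confound is not in the analysis. The larger obstacles to Problem Statement 2 are the absent white-light analysis and the biopsy of NBI-identified areas only, and both would remain whatever the order. This stands. Repairing them would nevertheless leave an NBI call made with knowledge of WLB, so the order is a separate limitation.

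A second reply is that the objective nowhere says NBI on its own, and that white light first is the natural order for Problem Statement 3. Both are correct. The objective is nevertheless silent on WLB, and nothing in the plan confines its conclusions to an add-on use.

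A third reply is that the criteria are vessel patterns, and earlier suspicion does not create a vessel pattern. This makes full carry-over hard to credit. It does not exclude closer attention to an area already noticed, or a readier call on a borderline pattern.

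Finally, the hospital's operating procedures and the research forms are not included. A white-light entry made before NBI is undescribed, not shown to be absent.

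A reader might infer that any NBI-versus-WLB contrast would favour NBI. The documents do not support that: carried-over white-light false positives lower NBI specificity, and the objective covers specificity, predictive values and AUC as well as sensitivity. A reader might also infer that the reported profile is that of WLB and NBI combined. It is not, because white-light-only areas are neither biopsied nor modelled.

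**Conclusion.** The point holds in a limited form. With a fixed order, a single operator and no described separation of the readings, the plan does not identify the profile of NBI uninformed by WLB, nor an unconfounded comparison for Problem Statement 2. What it can describe is NBI performed after, and with knowledge of, white light.

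No magnitude can be derived from the documents. Carry-over would tend to raise detection and lower specificity, its net effect on accuracy is unknown in sign, and the inflation of detection is zero if WLB detections are nested within NBI detections. A figure for the inflation of NBI sensitivity should not be quoted, since it would rest on assumed accuracies and assumed independence.

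The conclusion assumes that both looks take place in one session, as the text implies, and that no undisclosed procedure closes the white-light call first. It is a matter of what may be claimed. The planned analyses of vascular patterns against histology can still be run.

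**What to change.** 1. Restate the index test in the objective as NBI inspection performed after, and with knowledge of, WLB. Make no stand-alone claim for NBI and no head-to-head claim against WLB, and amend Problem Statement 2 to match.
2. Record and close the white-light call for each area on the research form before NBI is activated. Label each NBI-identified biopsied area as *already suspicious on WLB* or *new on NBI*, and report dysplasia yield (positive predictive value) separately for the two groups. Present the *new on NBI* group as the incremental yield, stating that it includes any second-look effect.
3. Do not present these results as comparative sensitivity, specificity or negative predictive value, because white-light-only areas have no histology.

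The cost is a rewording and a form entry per area, with no extra biopsy, procedure or staff. The stand-alone claim is given up. The document is dated late October 2023 and recruitment runs from March to December 2023, so a new entry would reach only the last patients. For those already examined, the label exists only if the white-light finding was noted at the time. The rewording applies to all patients and needs no new data.

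### Histology is described only for NBI-identified areas, so on the natural reading the sensitivity, specificity and NPV of NBI bronchoscopy, and its relative accuracy against white light, cannot be estimated

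*Combined protocol and SAP*

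**What the plan says.** - **Target.** Section 3, Research Objectives, sets out to determine the AUC and the "sensitivity, specificity, positive predictive value, and negative predictive value) of NBI bronchoscopy in detecting bronchial squamous dysplasia" in lung tumor patients.
- **Comparison.** Problem Statement 2 asks "How does the diagnostic profile of NBI bronchoscopy compare with standard bronchoscopy (white light bronchoscopy, WLB"). Problem Statement 3 asks "Can the addition of NBI to standard bronchoscopy procedures improve diagnostic accuracy".
- **Order of inspection.** Section 4, Sampling Technique: "Bronchoscopy was initially performed under the white light, followed by the activation of the NBI feature for airway inspection". No criteria for an abnormal white-light finding are given.
- **Source of histology.** The same section: "Biopsies were obtained from areas identified through NBI bronchoscopy findings". It then adds that "the criteria for bronchoscopy images suspected for dysplasia included the presence of dotted vessels, capillary loops, tortuous vessels, and abrupt ending vessels". The one explicit exclusion is "No biopsies were conducted on infiltrative neoplasms or tumors". The hospital procedure governing biopsy is cited but not reproduced.
- **Analysis.** Section 5 relates each NBI vascular pattern to histology, fits all patterns together, derives a prediction score and reports its AUC. It contains no WLB variable and no adjustment for areas without histology.
- **Unit.** "The minimum sample size required was 110 participants", whereas biopsies are of areas. Whether the analysis is by area or by participant is not stated.

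**The concern.** A diagnostic accuracy study needs the reference standard in test-negative as well as test-positive units. Here the test under study appears to decide which tissue reaches the pathologist. If only NBI-suspicious areas were biopsied, the study learns how often a suspicious area is dysplastic, but nothing about dysplasia in areas that NBI passed over.

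Two consequences follow. First, sensitivities, specificities or NPVs of individual patterns or of the score could be reported as those of NBI bronchoscopy itself, although they describe only areas that NBI had already selected. Second, the WLB comparison in Problem Statement 2 would be one-sided: an area abnormal on white light but normal on NBI has no histology, so verified dysplastic areas found by NBI can never be fewer than those found by WLB, whatever the truth.

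**Working it through.** **Inputs from the documents:** the five target measures, the single described biopsy source, the four vessel patterns, and 110 participants. The inputs behind 110 (expected accuracy, precision, prevalence) are not given, so it cannot be reproduced uniquely. One assumed set that fits is accuracy 0.80, precision 0.15, prevalence 0.25: 1.96² × 0.80 × 0.20 / (0.15² × 0.25) = 109.3, rounded up to 110. The point does not turn on this, since a larger sample would not fill an empty cell. All other rates below are assumptions. They show what cannot be identified; they are not an expected bias.

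**Step 1: the 2×2 table.** If only NBI-positive areas have histology, TP and FP are observed, FN and TN are not. PPV = TP/(TP+FP) is estimable. Taken naively, sensitivity = TP/(TP+0) = 100%, specificity = 0/(0+FP) = 0% and NPV = 0/0, whatever the true values.

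**Step 2: area-level sensitivity.** With r unverified dysplastic areas per verified one, sensitivity = 1/(1+r). For r = 0, 0.25, 0.5 and 1 this is 100%, 80%, 67% and 50%. The data say nothing about r.

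**Step 3: participant-level bounds.** Suppose m of 110 participants have no biopsied area and count as NBI-negative. The lowest sensitivity is TP/(TP+m), the highest specificity m/(m+FP). The other limits are 100% and 0%, and NPV runs from 0% to 100%. Sampling error and dysplasia elsewhere in the airway are ignored.

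| m | Dysplasia among those biopsied | TP, FP | Lowest sensitivity | Highest specificity |
|---|---|---|---|---|
| 11 | 40% | 40, 59 | 40/51 = 78% | 11/70 = 16% |
| 22 | 40% | 35, 53 | 35/57 = 61% | 22/75 = 29% |
| 33 | 40% | 31, 46 | 31/64 = 48% | 33/79 = 42% |
| 11 | 80% | 79, 20 | 79/90 = 88% | 11/31 = 35% |
| 22 | 80% | 70, 18 | 70/92 = 76% | 22/40 = 55% |
| 33 | 80% | 62, 15 | 62/95 = 65% | 33/48 = 69% |

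The specificity ceilings depend heavily on the assumed dysplasia rate.

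**Step 4: patterns and score.** Assume four independent patterns, each present in a share pd of dysplastic and pn of non-dysplastic areas. An area with any pattern is biopsied; a share s of no-pattern areas is biopsied too. With P0 = (1−pn)⁴, the specificity of one pattern among biopsied areas is 1 − pn/(P0·s + 1 − P0). For pn = 0.2 and s = 0: P0 = 0.4096, and 1 − 0.2/0.5904 = 66%, against 80% over all areas.

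| pd / pn | Specificity, all areas | Biopsied, s = 0 | Biopsied, s = 0.5 | AUC of pattern count: all areas | s = 0 | s = 0.5 |
|---|---|---|---|---|---|---|
| 50% / 20% | 80% | 66% | 75% | 0.811 | 0.749 | 0.791 |
| 40% / 10% | 90% | 71% | 85% | 0.834 | 0.738 | 0.823 |
| 60% / 30% | 70% | 61% | 66% | 0.801 | 0.762 | 0.785 |

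With correlated patterns (latent correlation 0.5) and s = 0, specificity among biopsied areas is 55%, 61% and 49%. The gap therefore depends on the biopsy rule that the plan does not state.

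**Step 5: Problem Statement 2.** Let a dysplastic areas be abnormal on both, b on NBI only, c on WLB only. The NBI:WLB detection ratio is (a+b)/(a+c). With a = 20, b = 10 and c unverified, the observed ratio is 30/20 = 1.50. If c were 0, 5, 10 or 15, the true ratio would be 1.50, 1.20, 1.00 or 0.86.

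**Step 6: Problem Statement 3.** If either test counts as positive, adding NBI gains b dysplastic areas, plus the false positives among NBI-positive/WLB-negative areas. Both lie in biopsied tissue and can be counted if WLB status was recorded by area. The proportional gain b/(a+c) cannot: with the same figures it is 10/20 = 50% at c = 0 and 10/35 = 29% at c = 15.

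**The case against.** **The premise is inferred.** A reader might infer that the protocol forbids biopsy of NBI-normal areas. It does not say so. The vessel criteria stand in a separate sentence, are not called the biopsy trigger or an exhaustive list, and the governing hospital procedure is not shown. This stands, and the conclusion is conditional on the natural reading. It does not remove the problem: the biopsy rule decides which measures exist, and the text gives no other source of histology.

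**The SAP may already define the diagnostic profile as that of patterns and score.** These have a computable sensitivity, specificity, PPV, NPV and AUC, and the analyses are legitimate, so it would be wrong to infer that Section 5 cannot be carried out. But Research Objectives speaks of NBI bronchoscopy without restriction, and results in areas chosen for their NBI appearance do not carry over to it.

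**Problem Statement 3 is not in the same position as 2.** It is tempting to say that both fail. Step 6 shows otherwise: the absolute extra detections and extra false positives are countable. Under an either-positive rule detections cannot fall even with full verification, so that one-sidedness is not a verification artefact.

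**The magnitudes are assumed.** This also stands. No document says that any participant lacked a biopsied area, and a countable set of all mucosal areas is not defined.

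**The missing WLB analysis and the unstated unit** would be gaps even with full verification. They matter here because the remedy cannot be written without them, but they add nothing to the severity of this point.

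**Conclusion.** The concern holds in conditional form. If histology came only from NBI-identified areas, as the text most naturally reads, three of the five measures in the objective (sensitivity, specificity and NPV of NBI bronchoscopy, suspicious against not suspicious) cannot be estimated, and no sample size would change that. PPV can be. Pattern, score and AUC results are valid among NBI-selected, biopsied areas only. Relative sensitivity and specificity of NBI against WLB are not identified, and the observed detection comparison cannot favor WLB. For Problem Statement 3, only the proportional gain and absolute accuracy are out of reach, provided that WLB status was recorded by area.

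The missing-cell result is exact under that reading; confidence in the reading itself is moderate. The illustrative figures rest wholly on assumed inputs, and the documents do not support quoting any of them as the size of a bias. The mismatch between objective and described design should be resolved before accuracy results are reported.

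**What to change.** Amend Research Objectives, Sampling Technique and the SAP. No further biopsies are needed.

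1. State the unit of analysis and whether any NBI-normal areas were biopsied. If they were, give the selection rule, the number biopsied and the number eligible, and correct for partial verification: Begg-Greenes or inverse-probability weighting, with known or estimated probabilities under a stated missing-at-random assumption. Add worst-case bounds as a sensitivity analysis. If NBI-normal areas were not counted, area-level bounds are not available.
2. If none were, either remove sensitivity, specificity and NPV of NBI bronchoscopy from the objective, or redefine it as the accuracy of vascular patterns and score among NBI-selected, biopsied areas. Report PPV with a 95% CI that allows for several areas per participant.
3. Label every pattern, score and AUC result as applying among NBI-selected, biopsied areas only, and report the number of participants with no biopsied area.
4. Limit Problem Statement 2 to NBI-selected areas and say that WLB-only abnormal areas are unverified. Answer Problem Statement 3 by the number of extra dysplastic areas and extra false positives in NBI-positive/WLB-negative areas, if WLB status was recorded by area.

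The cost is a few sentences, some rewording and one table. The downside is a narrower claim: no sensitivity, specificity or NPV for NBI bronchoscopy as a whole unless NBI-normal areas were verified.
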